9.2 Discussion of Study Design, Including Choice of Control Groups

9.2.1 Overview

This study is a multicenter, multiple-dose, double-blind, placebo-controlled, parallel-group study in subjects with EAD including MCI due to AD and the early stages of mild AD, aiming to randomize a total of 1330 subjects across 2 treatment groups, (placebo, 50 mg per day E2609) for 24 months. The maximum estimated duration for each subject on study is anticipated to be approximately 29 months (ie, 2-month Prerandomization Phase, followed by 24 months of treatment and a 3-month Follow-Up Phase).

As currently there is no cure for AD, there is no active or positive control for this study as at this time, no known way of slowing the progression of this disease, and no approved treatment available to reverse the deterioration of AD.

The primary endpoint of this study is to evaluate the effects of E2609 compared to placebo on the CDR-SB score. This endpoint is widely used in AD trials as a global measure of disease progression. The instrument is rated after a semi-structured interview with the subject and a study partner, and does not directly rely on psychometric tests, thus avoiding learning effects. One important factor associated with the use of the CDR-SB is that it is designed to incorporate cognitive and functional components; changes in the CDR-SB score reflect changes in both components. The clinical researcher separately interviews the subject and a study partner in order to assess changes in the subject's performance relative to their

premorbid performance on 6 domains: memory, orientation, judgment and problem solving; community affairs, home and hobbies, and personal care. Each domain is scored as 0 (none), 0.5 (questionable) except for personal care, 1.0 (mild), 2.0 (moderate), or 3 (severe). Two overall scores can be derived – a calculated global score using a standardized algorithm and a cumulative score summing the boxes. The cumulative score or CDR-SB is a well-described, validated, and reliable measure of change through the course of AD and has been proposed as a suitable single outcome measure for AD trials in dementia and pre-dementia populations.

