or FAQ are conducted, the investigator will determine whether the study partner must attend in person or whether telephone contact will be suitable, and will base this determination upon the functional ability of the subject among other factors.

- o Disease staging will be performed every 3 months. The site clinician is required to confirm the staging of disease, ie for subjects who were, at Screening, not clinically staged as dementia, does the subject still meet the definition of MCI due to AD or have they progressed into the stage of clinical dementia. This staging decision will be verified via a central review process and adjudicated if necessary. Adjudication will only occur when there is a discrepancy between the diagnosis and clinical disease staging made by the site compared to that determined by the central review process; moreover, where adjudication is required, it will be undertaken by an independent assessor(s). (revised per Amendment 01)
- p The clinical assessment of suicidality will require input from both the subject and the study partner
- q There are 3 components to the EQ-5D as follows: (1) in the subject by self report, (2) in the study partner by self report, (3) in the subject by proxy using the study partner
- r There are 2 components to the QOL-AD as follows: (1) in the subject by self report, (2) in the subject by proxy using the study partner
- s MRI scans are to include vMRI and fMRI sequences and will be read by an approved central reader. MRI imaging will be conducted on separate days from the scheduled visits. MRI imaging should be conducted within the 7 days before Visits 9 and 13. In the event of an Unscheduled Visit, the investigator in consultation with the Medical Monitor will determine whether or not a safety MRI should be conducted. If an ED Visit takes place, an MRI is to be conducted if not already performed during the preceding 90 days.
- t PET scanning (if subject has consented to optional substudy) will be performed with a locally approved amyloid β imaging agent, eg, Amyvid, if available or an agent under clinical investigation if no agents are approved locally; the imaging agent must remain unchanged for an individual subject throughout the study. A PET scan will only be performed at an ED Visit if the subject has been treated with study drug for at least 39 weeks.

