
For any given subject, every effort should be made to ensure that the diagnosing clinician

(responsible for the initial diagnosis and for disease staging) remains unchanged throughout the study. Similarly, every effort should be made to ensure that for any given subject, the CDR rater remains unchanged throughout the study. (revised per Amendment 03)

The following health-related quality of life assessments will also be collected at the Screening Visit and will provide baseline values for the study: EQ-5D (administered to both the subject and the study partner), QOL-AD (administered to both the subject and the study partner), and the Zarit's Burden Interview. The study partner needs to be available either in person or via telephone for these assessments.

Subjects will also be evaluated on the Columbia Suicide Severity Rating Scale (C-SSRS) for eligibility.

Following these initial assessments, blood will be collected from all subjects for clinical laboratory tests, AD exploratory biomarker analysis, and mandatory pharmacogenomics (PGx) analysis of *ApoE* genotype. A subset of PGx specimens may also be tested for N-acetyltransferase 2 (NAT2). (revised per Amendments 01 and 03) Vital signs and weight will be recorded, and a single 12-lead ECG will be conducted. A complete physical examination with dermatologic review and a full neurologic exam will be conducted. Additionally, a serum pregnancy test for females of child-bearing potential will be performed.

Subjects who pass the initial clinical and safety screen for eligibility will be then assessed via magnetic resonance imaging (MRI) for brain abnormalities that may exclude study participation. An additional scanning sequence for vMRI assessment, along with sequences for task-free resting fMRI, will be run immediately following the eligibility MRI sequences in all subjects. The MRI assessments conducted during Screening will also be used as the baseline MRI assessments for the respective measures.

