7. Subjects must have been on stable doses of all other (ie, non-AD related) permitted concomitant medications for at least 4 weeks before Randomization, except for medications that are administered as short courses (eg, up to 3 weeks unless discussed and agreed with the medical monitor) of treatment (eg, anti-infectives, oral steroids) or which are to be used on a Pro re nata (PRN) basis. Subjects who require a short course of treatment, such as anti-infectives or oral steroids, may be randomized once the acute illness has completely resolved, even if the concomitant medication continues.
8. Must have an identified study partner (defined as a person able to support the subject for the duration of the study and who spends at least 8 hours per week with the subject). The study partner must be literate and able to provide written informed consent. (revised per Amendment 03) In addition, this person must be willing and able to provide follow-up information on the subject throughout the course of the study. This person must, in the opinion of the investigator, spend sufficient time with the subject on a regular basis such that they can reliably fulfill the requirements of being a study partner. A study partner need not be living in the same residence with the subject. For such a study partner not residing with the subject, the investigator has to be satisfied that the subject can contact the study partner readily during the times when the study partner is not with the subject. Study partners need to provide input to the following assessments: CDR, FAQ, EQ-5D, QOL-AD, Zarit's Burden Interview, NPI-10, and the clinical assessment of suicidality. Consideration can occur for the investigator to decide whether the study partner can provide information over the telephone or whether the study partner must attend the study visits in person with the subject.
9. Provide written informed consent. Subjects must, in the investigator's judgment, have the capacity to consent (capacity to consent should be determined in accordance with applicable professional standards and local laws/regulations). (revised per Amendment 03)

Extension Phase (revised per Amendment 05)

1. Subjects who complete the 24-month Treatment Period and the 3-month Follow-up Period (Visit 15) of the Core Study, and whose Visit 15 falls within a 4-week window from the start of the Extension Phase. Subjects who discontinue study drug early are not considered to have 'completed' the Core Study.

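### The investigator may choose in-person or telephone contact with the study partner at each CDR and FAQ visit partly on the subject's function, so how the primary endpoint is measured may follow the outcome; the likely effect is small and the remedy cheap.

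*Protocol*

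**What the plan says.** Note n to Table 3 (Protocol 9.5.2.1) covers visits at which the CDR or FAQ is done. The investigator is to settle if the partner must come to the clinic or "whether telephone contact will be suitable, and will base this determination upon the functional ability of the subject among other factors". The note stands in both the original text and the text marked as revised per Amendment 01. In the Version 7.0 synopsis, inclusion criterion 8 keeps a general discretion: "Consideration can occur for the investigator to decide whether the study partner can provide information over the telephone". It names neither functional ability nor a decision at each visit. The Version 7.0 schedule notes are not in the part shown.

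The CDR is done every 3 months, so the choice recurs through treatment. Section 9.2.1 says of the CDR: "The instrument is rated after a semi-structured interview with the subject and a study partner". It says of CDR-SB that "it is designed to incorporate cognitive and functional components". FAQ is rated by the study partner (9.5.1.3.1).

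The protocol standardises comparable sources of variation: time of day for the subject's part of the tests, the PET agent, the clock time of the lumbar puncture and, since Amendment 03, the rater: "every effort should be made to ensure that for any given subject, the CDR rater remains unchanged throughout the study". No text shown extends this to the mode of partner contact or requires the mode to be recorded. The stated primary MMRM has no term for it.

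**The concern.** The only criterion named for choosing how the partner is interviewed is something that CDR-SB and FAQ themselves score. A site following the note could reasonably telephone the partner of a stable subject and call in the partner of one who is declining. Mode would then be a post-randomisation variable related to outcome, and to treatment if the drug changes outcome.

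If partners report differently by telephone, that difference enters the change from baseline whenever the mode at month 24 is not the mode at baseline. It enters unequally by arm if the arms decline at different rates. The same route reaches FAQ, CDR-based time to worsening and, in Version 7.0, ADCOMS, which uses CDR items. If the mode is not recorded, no later analysis can examine any of this.

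**Working it through.** **Inputs.** Version 7.0 sample size rationale: placebo change 1.46, SD 2.05, 25% reduction, 30% dropout, 90% power, two-sided alpha 0.05. That paragraph also mentions a mean of 1.5. The earlier texts (9.7.2) use 1.75 with the same SD, reduction, dropout and power. The documents give no effect of mode.

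**Plan's own figures.** n per arm = 2(1.960 + 1.282)² × SD² / difference².
- Version 7.0: difference 0.25 × 1.46 = 0.365; n = 663; 663/0.7 gives 948 per arm, 1896 in total against the stated 1900. A mean of 1.5 would give 1798, so 1.46 is the figure behind 1900.
- Earlier texts: difference 0.25 × 1.75 = 0.4375; n = 462; 462/0.7 = 660 per arm, 1320 in total against the stated 1330.

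Both reproduce closely. The sample size is not in dispute.

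**Largest mode imbalance between arms.** Suppose every subject whose 24-month change exceeds one cut-off has the partner seen in person, and everyone else has the partner telephoned. With normal changes and a common SD, the arms differ most when the cut-off lies midway between the two means:
- Means 1.46 and 0.75 × 1.46 = 1.095; midpoint 1.2775.
- Maximum imbalance = 2Φ(0.365 / (2 × 2.05)) − 1 = 2Φ(0.089) − 1 = 0.071, or 7.1 percentage points.
- With the 1.75 inputs: 2Φ(0.4375 / 4.10) − 1 = 0.085. A simulation with cut-offs at 1 and 2 points gave 0.082 and 0.083.

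**Distortion of the difference** = imbalance × mode shift. The shift is assumed at 0.25 to 0.5 CDR-SB points:
- 0.071 × 0.25 = 0.018, which is 4.9% of 0.365.
- 0.071 × 0.5 = 0.036, which is 9.7% of 0.365.

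The difference widens if in-person reports score worse and narrows if they score better.

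**Power.** In the simulation with the 1.75 inputs, shifts from −1 to +1 point moved the difference from 0.436 to between 0.354 and 0.519. Power stayed between 0.89 and 0.90, because the SD moved with the difference.

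**Noise.** If half the subjects change mode in the same direction for reasons unrelated to outcome, a 0.5-point shift adds 0.5² × 0.5 × 0.5 = 0.0625 to a variance of 2.05² = 4.2025, about 1.5%.

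**No treatment effect.** The two outcome distributions coincide, so the share seen in person is the same in both arms and the distortion is zero.

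**The case against.** Function is one factor among others, so mode may follow the outcome but need not. Only the partner's part of the CDR is affected: "The clinical researcher separately interviews the subject and a study partner in order to assess changes in the subject's performance". Investigators are blinded to treatment. Flexible contact helps to retain partners who live elsewhere, in a trial that already assumes 30% dropout. Rater guides and CRF guidelines are not shown and may deal with mode. Some scales are audio-recorded for possible central review. All of this stands, and it limits the size and certainty of the point. It does not remove the instruction in note n to weigh function.

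Some stronger readings are tempting but not supported:
- **Declining subjects will always have the partner in clinic, or practice differs by site habit.** The note does not say the first, and nothing shown bears on the second.
- **The bias could reach a fifth of the planned effect.** That takes an imbalance near 15 points (0.15 × 0.5 = 0.075, or 21% of 0.365). A rule driven by CDR-SB change cannot produce more than about 7 points at the planned effect.
- **It could produce a false positive.** With no treatment effect, this mechanism gives equal mode mix in both arms.
- **Version 7.0 demonstrably kept the functional-ability rule while fixing the rater.** Its schedule notes are not shown. The revision log lists no change to the rule, but that is not the same as seeing the current text.

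**Conclusion.** The point holds in a limited form. Note n ties the mode of the partner interview to a quantity that the primary endpoint scores, and nothing shown holds the mode constant or has it recorded. The consequence is a modest risk to the size of the estimated effect and a little extra noise. It does not threaten type I error through this route, and the loss of power is negligible.

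The bound of about 0.02 to 0.04 points (5 to 10% of 0.365) rests on an assumed mode shift of 0.25 to 0.5 points that is the same for all subjects, normal changes with SD 2.05, and a choice of mode that depends on treatment only through the CDR-SB change. A discretionary choice with other factors in play would normally give less. A larger mode shift would give proportionately more.

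**What to change.** Amend note n, and its counterpart in the Version 7.0 schedule if the wording survives there, for CDR and FAQ only:
- Sites make every effort to keep the partner-interview mode used at Visit 2 for that subject at all later visits, above all Visit 13.
- The subject's functional ability is not a reason to change the CDR or FAQ interview mode.
- A CDR by the other mode is preferred to a missed one. An absolute rule at Visit 13 could lose primary-endpoint data.

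Cross-refer to this from inclusion criterion 8. Leave 9.5.1.6 unchanged, because its similar sentence governs EQ-5D, QOL-AD and Zarit's interview.

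Record the mode on the eCRF at every CDR and FAQ, and tabulate it by arm and visit. Add a supportive analysis that keeps all data, for example the primary MMRM repeated over a range of assumed mode shifts. CDRs whose mode changed should not be excluded, since that would select on a variable related to outcome.

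The cost is a wording change, one eCRF field and some inconvenience to partners.

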9.5.2.2 Description of Procedures/Assessments Schedule

Please refer to [Table 2](#) and [Table 3](#) for the timings of the procedures and assessments to be performed during the study. Screening assessments will be organized into 5 tiers (see [Table 2](#)). See [Section 9.5.1](#) for a full description of the procedures and assessments to be performed during this study.

[Table 4](#) presents the number of blood and CSF samples, and the total volume of blood and CSF that will be collected throughout the study. Additional samples may be taken at the discretion of the investigator if the results of any tests fall outside reference ranges or if clinical symptoms necessitate testing to ensure subject safety.

Table 4 Summary of Blood and CSF Sample Volumes

Assessment	Total Number of Collection Time Points	Sample Volume, Number of Time Points x Volume per Collection (mL)		Total Volume (mL)
		Screening Visits	Treatment and Follow-Up Periods	
Blood				
Clinical chemistry	15	1×5 mL	14×5 mL	75 mL
Serum pregnancy test at Screening (females of childbearing potential only)	1	can use blood drawn for clinical chemistry	None	no additional volume
Hematology	15	1×2 mL	14×2 mL	30 mL
Thyroid function tests (thyroid stimulating hormone, free triiodothyronine and free thyroxine)	1	1×5 mL	None	5 mL
Viral screen at Screening (Hepatitis B and C)	1	1×5 mL	None	5 mL
Viral characterization at Visit 2 (previous exposure to CMV, HSV1, HSV2, etc.)	1	None	1 x 4 mL	4 mL
Vitamin B12 at Screening	1	1×5mL	None	5 mL
Blood for immunologic assessments, including isolation of PBMCs for storage and later testing (revised per Amendment 01)	15	1×20 mL	14×20mL	300 mL
Blood for immune status	8	none	8×5 mL	40 mL
PD and exploratory biomarker sample	8	1×20 mL	7×12 mL	104 mL
PK analysis	8	1×4 mL	7×4 mL	32 mL
Pharmacogenomic sample	1	1×3 mL	None	3 mL
All blood samples, total volume collected		69 mL	534 mL	603 mL
CSF				
Amyloid eligibility	1	1×12 mL	None	12 mL
PD / PK (optional longitudinal substudy)	1	none	1×12 mL	12 mL

CMV = cytomegalovirus, CSF = cerebrospinal fluid, HSV1 = herpes simplex virus 1 (orolabial herpes), HSV2 = herpes simplex virus 2 (genital herpes), PBMC = peripheral blood mononuclear cells, PD = pharmacodynamics, PK = pharmacokinetic.

9.5.3 Appropriateness of Measurements

All clinical assessments are standard measurements commonly used in studies of AD.

Standard safety assessments incorporated into this protocol include assessment of AEs and SAEs, measurement of vital signs, clinical laboratory assessments, physical examinations (including dermatologic review), neurologic examinations, ECG measurements, assessments of suicidal thinking and behavior, and MRI.

9.5.4 Reporting of Serious Adverse Events, Pregnancy, and Events Associated with Special Situations

9.5.4.1 Reporting of Serious Adverse Events

All SAEs, regardless of their relationship to study treatment, must be reported on a completed SAE form by email or fax as soon as possible but no later than 24 hours from when the investigator becomes aware of the event.

SAEs, regardless of causality assessment, must be collected up to 12 weeks after the last dose of study drug. All SAEs must be followed to resolution or, if resolution is unlikely, to stabilization. Any SAE judged by the investigator to be related to the study treatment or any protocol-required procedure should be reported to the sponsor regardless of the length of time that has passed since study completion.

The detailed contact information for reporting of SAEs is provided in the Investigator Study File.

For urgent safety issues, please ensure all appropriate medical care is administered to the subject and contact the appropriate study team member listed in the Investigator Study File.

It is very important that the SAE report form be filled out as completely as possible at the time of the initial report. This includes the investigator's assessment of causality.

Any follow-up information received on SAEs should be forwarded within 1 business day of its receipt. If the follow-up information changes the investigator's assessment of causality, this should also be noted on the follow-up SAE form.

Preliminary SAE reports should be followed as soon as possible by detailed descriptions including copies of hospital case reports, autopsy reports, and other documents requested by the sponsor.

The investigator must notify his/her IRB/IEC of the occurrence of the SAE in writing, if required by their institution. A copy of this communication must be forwarded to the sponsor, or its designee, to be filed in the sponsor's Trial Master File.

9.5.4.2 Reporting of Pregnancy and Exposure to Study Drug Through Breastfeeding

Any pregnancy in which the estimated date of conception is either before the last visit or within 28 days of last study treatment, or any exposure to study drug through breastfeeding during study treatment or within 28 days of last study treatment, must be reported.

If an adverse outcome of a pregnancy is suspected to be related to study drug exposure, this should be reported regardless of the length of time that has passed since the exposure to study treatment.

A congenital anomaly, death during perinatal period, an induced abortion, or a spontaneous abortion are considered to be an SAE and should be reported in the same time frame and in the same format as all other SAEs (see Reporting of SAEs [Section 9.5.4.1]).

Pregnancies or exposure to study drug through breastfeeding must be reported by fax or email as soon as possible but no later than 1 business day from the date the investigator becomes aware of the pregnancy. The contact information for the reporting of pregnancies and exposure to study drug through breastfeeding is provided in the Investigator Study File. The Pregnancy Report Form must be used for reporting. All pregnancies must be followed to outcome. The outcome of the pregnancy must be reported as soon as possible but no later than 1 business day from the date the investigator becomes aware of the outcome.

A subject who becomes pregnant must be withdrawn from study treatment.

9.5.4.3 Reporting of Events Associated with Special Situations

9.5.4.3.1 REPORTING OF ADVERSE EVENTS ASSOCIATED WITH STUDY DRUG OVERDOSE, MISUSE, ABUSE, OR MEDICATION ERROR

AEs associated with study drug overdose, misuse, abuse, and medication error refer to AEs associated with uses of the study drug outside of that specified by the protocol. Overdose, misuse, abuse, and medication error are defined as follows:

Overdose	Accidental or intentional use of the study drug in an amount higher than the protocol-defined dose
Misuse	Intentional and inappropriate use of study drug not in accordance with the protocol
Abuse	Sporadic or persistent intentional excessive use of study drug accompanied by harmful physical or psychological effects
Medication error	Any unintentional event that causes or leads to inappropriate study drug use or subject harm while the study drug is in the control of site personnel or the subject.

All AEs associated with overdose, misuse, abuse, or medication error should be captured on the Adverse Event eCRF and also reported using the procedures detailed in Reporting of SAEs (Section 9.5.4.1) even if the AEs do not meet serious criteria. Abuse is always to be captured as an AE. If the AE associated with an overdose, misuse, abuse, or medication error does not meet serious criteria, it must still be reported using the SAE form and in an expedited manner but should be noted as nonserious on the SAE form and the Adverse Event eCRF.

